4.3.2 Intervention

At the completion of the baseline phase, all participants will receive an email to an educational website where they can learn about the dangers of distracted driving (<http://endddd.org>). Teens will also complete a survey.

Cellcontrol will remotely flip the participant's DriveID into a cellphone blocking mode for those in the three blocking conditions of the study on the first day of the intervention period. Teens randomized into the control group will continue with DriveID as is (information regarding cell phone use will continue to be collected, but no blocking will occur). In the blocking conditions, the phone will lock when being used while driving, but the locking function can be overridden.

Coded data on primary and secondary endpoints will be automatically uploaded daily whenever the phone has a Wi-Fi or cellular data connection to the Cellcontrol server and then exported through an encrypted, secure internet connection to Penn's Way to Health IT Platform for management and analysis via linkage of a study ID.

All parents will have the option to check teen's phone use while the vehicle is in motion on the website (<https://account.cellcontrol.com/login.php>) during weeks five to ten. Parents in the opt-out blocking with parental notification group will receive a notification every time the phone is being used while the vehicle is in motion.

4.3.3 Follow-up Phase

At the completion of the Intervention phase, participants will receive a text message and/or email notification that they are eligible change the configuration settings to any of the four conditions tested in the trial. Changes can be made by logging into the Cellcontrol online portal. We will collect data on what configuration the participants choose to make during the 2-week follow-up phase. If a participant does not choose a configuration for the follow-up phase after 1 week, the default setting will be to stay in the configuration they are currently in.

4.3.4 Debriefing

At the completion of the follow-up phase or upon voluntary withdrawal from the trial, the participant will be instructed to complete an online survey administered through Penn's Way to Health IT platform asking about user satisfaction with the device. They will receive a link

to the survey through email. If necessary, they may receive reminder calls, emails, or text messages from members of the study team for a one month period following study completion. The purpose of the survey will be to debrief the participant's experience with the trial, cellphone blocking technology, and suggestions for designing a better trial. For subjects that withdrawal prematurely, we will ask about what factors contributed to their decision to withdraw early.

For participants who complete the trial, a member of the study team may contact them to complete a brief phone interview.

4.4 Subject Completion/Withdrawal

Participants may withdraw from the study at any time. They may also be discontinued from the study at the discretion of the Investigators at any time.

5 STUDY EVALUATIONS AND MEASUREMENTS

5.1 Confirmation of Eligibility

Members of the research team will confirm the eligibility of potential subjects based on the inclusion/exclusion criteria noted in Section 3.4 after the online assent process. A parent or guardian will first need to create an account on the Way to Health platform and complete consent online. Once consent is obtained, teens will need to create an account on the Way to Health platform and complete assent. After the participant provides assent, they will be presented with a survey to confirm eligibility. If they are eligible, an intake survey will be available for teens to complete. A study team member will contact participants to confirm eligibility (which will be recorded and retained for all individuals). If subjects are not eligible, no other study procedures will occur.

5.2 Intake Survey

We will collect the following information on each subject:

- Demographic characteristics
- First two digits of the teen's driver's license number
- Month and year of birth
- Last four digits of the teen's social security number (for UPenn's reporting purposes)
- Opinions and perceptions on texting while driving and associated technology

5.3 Cellcontrol Data

Cellcontrol requires users to enter in basic information to set up the account policy. This includes:

- Username
 - Password
 - Name
 - Phone number
-

- Email

The Cellcontrol app currently tabulates the following data which are uploaded securely to the Cellcontrol server:

- Phone talk time while driving
- Phone usage time while driving (non-talk time phone unlocked and being used for apps, texts, email, etc).
- Phone unlocks while driving
- Speed the car is traveling when the phone is unlocked
- Incidence of hard decelerations converted to a “driving score” and hard accelerations converted to an “eco score”
- Number of incoming calls and texts that are blocked
- GPS, accelerometer, and timestamp data

5.4 Post-Baseline Survey

We will collect self-report information on each subject’s driving behaviors for the past thirty days in which they were driving in the baseline period. Information includes how often they report driving and self-report cell phone use.

5.5 Teen End of Study Survey

We will survey participants via the Way To Health platform. The survey will be constructed in Qualtrics, an online survey tool used by Way To Health, to elicit feedback on the cellphone locking technology. Teen subjects will be asked to report:

- Their feedback on using the cellphone blocking technology
- Feedback on settings/configurations of the cellphone blocking technology
- Perceptions of whether their safety had improved with the use of the technology
- Suggestions for improving the technology and the research study
- Suggestions for future interventions to promote engaged driving

A member of the study team may contact participants over the phone to elaborate upon responses to the end of study survey questions.

5.6 Teen Semi-Structured Interview

We may call participants upon completion of the follow-up period to complete a semi-structured phone interview. The interview will be conducted by a member of the study team and will be recorded by the Penn Mixed Methods Research Lab. The interview will last approximately twenty minutes. Teen subjects will be asked questions regarding:

- Feedback on each intervention phase of the study (baseline, intervention, and follow-up)
 - Suggestions for preventing cellphone distractions while driving
-

- If they will continue to use this technology

5.7 Safety Evaluation

This is a minimal risk, behavioral intervention study. Physical risk is no more than the risks already caused by distracted driving from handheld cellphone use. The intervention directly lowers the risk of distracted driving by blocking incoming phone calls and texts and locking the phone while the participant is driving. The participant may unlock the phone in any of the conditions with the swipe of a finger where they will then be brought to their typically screen. If participants have their phone password protected, they will still need to enter their password in order to use the phone. The extra swipe to dismiss the cellphone blocking technology is no more dangerous than unlocking the phone normally.

Participants will have no interaction with the physical DriveID device after installation. There are no expected serious adverse events related to the intervention or participation in this study.

6 STATISTICAL CONSIDERATIONS

This is a pilot trial with the purpose of demonstrating the feasibility of conducting this type of research and generating data in order to estimate sample sizes for future trials.

6.1 Primary Endpoint

Frequency of phone unlocks while driving (unlocks/hour)

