Forty-four participants each received a cell phone filtering/blocking application on their employer-provided cell phones for 9 weeks. During the first and last 3 weeks, cell phone activity including calling, text messaging and application use was simply recorded in the background. During the middle 3 weeks, the cell phone filtering/blocking software was active, meaning that anytime the application sensed that the phone was moving faster than the pre-set speed threshold, all phone activity was blocked. Objective data on participants' phone use behavior and subjective data (from a questionnaire) on participants' acceptance were collected. Additionally, the impact on an organization attempting to implement a similar program employing cell phone filtering/blocking was examined. During the blocking period, participants initiated a higher proportion of their calls when stopped than when the blocking software was inactive. Also, during the blocking period, participants answered a much smaller proportion of incoming calls while driving, and outgoing calls were placed at a lower mean speed. Participants were neutral in their opinions on whether they received a safety benefit from the cell phone blocking.

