2 STUDY OBJECTIVES

The purpose of the study is to demonstrate feasibility of conducting a field trial of cellphone blocking technology in teen drivers to calculate sample sizes for future trials and generate preliminary data for funding applications. Primarily, the proposed is measuring whether activation of a cellphone blocking device results in a decrease in the total proportion of time in which a cellphone is being used at non-zero speeds by teen drivers.

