2.2 Secondary Objectives (or Aim)

The secondary objectives are to:

- Measure whether activation of a cellphone blocking device (DriveID) results in a decrease in the total proportion of time in which a cellphone is being used at non-zero speeds by teen drivers compared with baseline cellphone use while driving.
-

- Measure the reasons cellphones are being used while driving at non-zero speeds among teens (calls, texts, smartphone apps, etc.)
- Measure teen satisfaction with the cellphone monitoring and blocking device
- Determine the incidence of handheld cellphone use while driving and its relationship to incoming text messages and driving conditions in a teen driver cohort.
- Measure the number of phone unlocks per hour of drive time
- Measure the speed of the car, acceleration, and spatial characteristics of phone unlocks (ex. on highways vs. at intersections)

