6.2 Secondary Endpoints

Total proportion of time the phone is in use at non-zero speeds

Seconds of phone use at non-zero speeds

Seconds of phone use while stopped

Number of incoming calls and texts that were blocked

Number of times participants make or receive a phone call, send or read a text message, and use any application while driving at non-zero speeds

Proportion of participants who switched to another blocking configuration in the Follow up period

Participant acceptance of cellphone blocking technology based on post-study survey

Incidence of handheld cellphone use and its relationship to incoming text messages and driving

In determining feasibility the following will be measured:

- Proportion of screen eligible who enroll
 - Number enrolled per month
 - Retention rates by study arm
 - Proportion of surveys completed
-

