6.3.2 Efficacy Analysis

The primary analysis will be based on an intention to treat approach and will include all subjects randomized at the beginning of the intervention period.

The primary efficacy endpoint will be the difference in frequency of cellphone unlocks per hour of driving between weeks 5 and 8 compared with baseline period weeks 2 to 4. The statistical analysis will use relative change models adjusted for age, sex, state, and presence of in-vehicle navigation and phone connectivity systems will compare % change in unlocks per hour with 95% confidence intervals in each intervention arm relative to control arm.

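### Does the primary unlock rate need a rule on whether unlocks at a stop count?

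*Combined protocol and SAP*

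**What the plan says.** Section 6.1 gives the primary endpoint as "Frequency of phone unlocks while driving (unlocks/hour". Section 6.3.2 analyses the "difference in frequency of cellphone unlocks per hour of driving between weeks 5 and 8 compared with baseline period weeks 2 to 4", as a percentage change in each blocking arm relative to control. Neither section puts a speed condition on the count or on the hours, and the plan does not define driving.

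Elsewhere the plan does condition on speed. Section 2 says that the study chiefly measures whether blocking leads to a "decrease in the total proportion of time in which a cellphone is being used at non-zero speeds by teen drivers". The secondary objectives in section 2.2 include "Measure the reasons cellphones are being used while driving at non-zero speeds among teens". Section 6.2 counts how often participants call, text or "use any application while driving at non-zero speeds", and it lists "Seconds of phone use while stopped" as an endpoint next to seconds of use at non-zero speeds. Section 2.2 also plans to describe car speed, acceleration and the "spatial characteristics of phone unlocks (ex. on highways vs. at intersections". Sections 7.1.2 to 7.1.4 have the blocking act on a moving vehicle, and in the parental-notification arm the alert follows overrides at non-zero speeds. Section 5.3 lists unlocks during driving, and the car's speed at an unlock, among the data that the app tabulates.

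**The concern.** The intervention works on a moving car, but the primary count seems to take in moments when the car stands still. If blocking leaves unlocks at stops unchanged, including them dilutes the percentage change. If teens hold back until a red light, the dilution is greater. The field study summarised in section 1.3 points that way for calls: under blocking, "participants initiated a higher proportion of their calls when stopped than when the blocking software was inactive".

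An analyst who counts every unlock in a drive and one who counts only moving unlocks could therefore report different effects for all three blocking arms. Section 6 says that the pilot is meant to inform the size of future trials, so the choice could carry over into those calculations.

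**Working it through.** There is no figure in the plan to reproduce. The check has four parts.

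**1. Does the wording settle the reading?** Sections 2.2 and 6.2 attach non-zero speeds to driving when they mean moving only. That qualifier would be redundant if driving already excluded stops. The unlock objective in section 2.2, expressed per hour of drive time, has no such qualifier; nor do sections 6.1 and 6.3.2. The plain reading is all unlocks within a drive. This is an inference and not a stated rule: section 4.3.2 says the phone locks during driving, where sections 7.1.2 to 7.1.4 refer to motion. However, section 5.3 names an app variable in almost the same words as section 6.1, so analysts would probably draw on one common variable. Its vendor definition is not given.

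**2. How far apart could the two counts be?** All inputs are assumptions; the documents give none of them.

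- B = baseline unlocks per hour, p = share of these at zero speed, r = fall in moving unlocks. Control and stopped unlocks are unchanged.
- Moving unlocks: B(1 − p) becomes B(1 − p)(1 − r). Stopped unlocks: Bp stays Bp.
- Reduction in all unlocks = r(1 − p). B cancels.

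| Assumed r | Assumed p | Moving-only reduction | All-unlocks reduction |
|---|---|---|---|
| 30% | 0% | 30% | 30% |
| 30% | 20% | 30% | 0.30 × 0.80 = 24% |
| 30% | 35% | 30% | 0.30 × 0.65 = 19.5% |
| 30% | 50% | 30% | 0.30 × 0.50 = 15% |

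Check with B = 20 and p = 50%: moving 10 to 7, stopped 10 to 10, total 20 to 17, a fall of 3/20 = 15%. The counts agree if p = 0, or if stopped and moving unlocks change by the same percentage.

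**3. Does the denominator matter?** If a share t of drive time is stopped, dividing by moving time instead of all drive time multiplies a rate by 1/(1 − t): 1.11, 1.25 or 1.43 for assumed t of 10%, 20% or 30%. If t is the same in weeks 2 to 4 and weeks 5 to 8, the factor stands in both rates and cancels from the percentage change.

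**4. Does the field study show a shift to stops?** Not by itself. Take p = 20% and r = 30% with no displacement. The stopped share rises from 20% to 0.20/(0.20 + 0.80 × 0.70) = 0.20/0.76 = 26.3%, only because moving events fell. A higher proportion at stops is what blocking would produce without any use being moved there. That study also concerned calls, with all phone activity blocked.

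**The case for a change.** The best case for a change is that the rule is missing, that it concerns the state in which the treatment acts, and that writing it down would cost a few sentences and one more run of the same model. Section 6.3.2 does specify a primary contrast with 95% confidence intervals, whatever the pilot status of the trial. Parents in the notification arm are alerted only to overrides in motion, which gives teens in that arm a particular reason to wait for a stop. One rule for all arms prevents unequal measurement but does not make the two counts estimate the same quantity.

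Much of this stands. The definition is absent, and the estimated percentage would differ between the counts unless one of the conditions in the working holds. What does not follow is that the plan is unsound without the addition. The formal primary objective in section 2.1 is feasibility. Time in use at non-zero speeds is a secondary objective with its own endpoint in section 6.2, and the unlock rate is listed as a separate objective, so the unlock count need not carry the non-zero-speed aim.

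Nor is the moving-only count plainly better. It rests on fewer events, so its interval may widen, and it would not show use that moved to stops. Carrying both as versions of the primary contrast invites selective reading. For sizing a later trial, either version could be taken from the planned data, provided speed is stored for each unlock, as section 5.3 suggests.

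**Conclusion.** This is a gap in definition that analysts can fill sensibly, and no change to the plan is called for. Counting every unlock in a drive is the natural reading. Used in the same way in all four arms and in both periods, it gives a valid randomised comparison of unlock rates. Section 9.1.1 has the analysts work without knowing the arms, so the convention can be settled without regard to the result.

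The all-unlocks percentage may be smaller than a moving-only one. The amount depends on the share of unlocks at stops, which the documents do not give, and it is zero if that share is zero. The illustrated range, 15% to 30% for a 30% fall in moving unlocks, rests wholly on assumed stop shares of 0% to 50% and no change at stops. The endpoints for moving and stopped use in section 6.2, with the unlock-speed objective in section 2.2, already cover much of the question. It is enough that the trial report states which unlocks and which hours were counted.

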6.2 Secondary Endpoints

Total proportion of time the phone is in use at non-zero speeds

Seconds of phone use at non-zero speeds

Seconds of phone use while stopped

Number of incoming calls and texts that were blocked

Number of times participants make or receive a phone call, send or read a text message, and use any application while driving at non-zero speeds

Proportion of participants who switched to another blocking configuration in the Follow up period

Participant acceptance of cellphone blocking technology based on post-study survey

Incidence of handheld cellphone use and its relationship to incoming text messages and driving

In determining feasibility the following will be measured:

- Proportion of screen eligible who enroll
 - Number enrolled per month
 - Retention rates by study arm
 - Proportion of surveys completed
-

6.3 Statistical Methods

6.3.1 Baseline Data

Baseline and demographic characteristics will be summarized by standard descriptive summaries (e.g. means and standard deviations for continuous variables such as age and percentages for categorical variables such as gender).

6.3.2 Efficacy Analysis

The primary analysis will be based on an intention to treat approach and will include all subjects randomized at the beginning of the intervention period.

The primary efficacy endpoint will be the difference in frequency of cellphone unlocks per hour of driving between weeks 5 and 8 compared with baseline period weeks 2 to 4. The statistical analysis will use relative change models adjusted for age, sex, state, and presence of in-vehicle navigation and phone connectivity systems will compare % change in unlocks per hour with 95% confidence intervals in each intervention arm relative to control arm.

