The objective of this study is to measure whether activation of a cellphone blocking device results in a decrease in the frequency of drives in which the phone is unlocked and the total proportion of time in which a cellphone is being used at non-zero speeds by teen drivers and to determine the incidence of handheld cellphone use while driving and its relationship to incoming text messages and driving conditions in a teen driver cohort.

Study Design:

Research participants will be recruited to take part in a randomized control trial. Participants' cellphone use will be observed during an initial baseline period. Participants will then be randomly assigned to one of four conditions (education only (control), opt-in blocking, opt-out blocking, and opt-out blocking with parental notification).

[figure not shown]
Setting/Participants:

High school students who are age 16 or 17 at the start of the study that drive an average of 4 trips per week and hold a valid driver's licenses will be recruited. Other inclusion criteria include living with a parent/guardian, having their own smartphone (iPhone 4S or newer or Android 4.3 or newer) with data plan, primarily driving one car, admitting to texting while driving at least once in the past month, do not currently use a cellphone blocking app or device, and that a parent will be willing to install the device and adjust the settings as necessary.

Study Interventions and Measures:

A cellphone blocking device (DriveID) will be mailed or given directly to participants. DriveID will measure all teen participant cellphone use while the cellphone is in the car for the first four weeks. During the intervention period (Weeks 5-8), participants will be placed into one of the four conditions (one control, three blocking) that they have been randomized to. At the beginning of Week 5, the participant's DriveID will either be flipped into a cellphone blocking mode where the phone will lock when being used while driving or remain in a control mode. A two week follow-up phase will occur after the intervention, during which participants may choose which group they would like to try. Surveys and an interview will also be administered as part of this study.

FIGURE 1: STUDY DIAGRAM

Measurements:

Cellphone use while driving	—————→		
Participant Survey	X	X	X*
Educational Information		X	
Interview			X

* Participant chooses mode for follow-up phase

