3.1.2 Baseline Measurement Period (4 Week Block)

DriveID will monitor all cellphone use while the teen driver's cellphone is in the car in which DriveID is installed. The application will run in the background, so there will be no observable changes to participants' cellphone functions. DriveID will capture GPS data throughout the baseline, intervention, and follow-up periods. At the completion of the fourth week, the teen participant will be instructed to complete an online survey administered through Penn's Way to Health IT platform asking about driving behaviors for the first thirty days of the study. Participants will have 2 weeks to complete this survey.

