3.1.3 Intervention Period (4 Week Block)

At the beginning of the intervention period (this will start within 2 business days of baseline measurement period survey completion), all participants will receive an email with a link to an educational website that raises awareness of the dangers of distracted driving (<http://endddd.org>). The Children's Hospital of Philadelphia has performed an independent evaluation of the educational content of the website and found it to be evidence based, and scientifically guided⁸.

DriveID will be used as a cellphone blocking device for those in the three cellphone blocking conditions where the phone will lock while driving, but the locking function can be overridden according to pre-set settings. DriveID will continue to monitor cellphone use while driving including how often the teen unlocks the cellphone as well as if they are using the phone for a call or other phone features. However, DriveID is not able to differentiate which phone features are being used.

The study team does not promote texting and driving and encourages all participants to drive safely.

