7.1.1 Education Only (Control) Group

Participants in the control group will complete the Baseline driving period, but at the end of Week 4, instead of DriveID flipping into a blocking mode, the device will remain at baseline settings. It will continue to collect information regarding cellphone use while driving in the background. There will be no observable changes to cellphone functions.

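### Does the weeks 5 to 8 window for the primary endpoint take in driving from before assignment and blocking?

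*Combined protocol and SAP*

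**What the plan says.** Section 6.3.2 sets the primary contrast as unlocks per hour "between weeks 5 and 8 compared with baseline period weeks 2 to 4", among subjects randomized when the intervention period begins. It does not say what event starts week 1.

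Two places put the switch at the boundary between weeks 4 and 5. The abstract (Study Interventions and Measures) has it "At the beginning of Week 5", and section 7.1.1 describes the control arm's position "at the end of Week 4, instead of DriveID flipping into a blocking mode". The abstract also names the period: "During the intervention period (Weeks 5-8), participants will be placed into one of the four conditions".

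Other sections describe a trigger. Section 3.1.2 issues a survey once week 4 is complete and adds: "Participants will have 2 weeks to complete this survey". Section 3.1.3 says of the intervention period that "this will start within 2 business days of baseline measurement period survey completion". Blocking is switched on "on the first day of the intervention period" (section 4.3.2), and section 9.1.1 draws the assignment as each participant reaches that phase. Section 4.3.2 lets parents view phone use "during weeks five to ten".

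**The concern.** A teen who takes ten days over the survey cannot be switched both at the start of calendar week 5 and after completing the survey. If the analyst counts weeks from the start of baseline, that teen's weeks 5 to 8 begin with unassigned, unblocked driving, and the same number of intervention days at the end go uncounted. Each blocking arm's percent change relative to control would then move toward zero.

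Section 6 says the pilot is meant to supply data for sizing later trials, so a diluted estimate could make those trials larger than needed. The window also defines the primary endpoint, where two analysts should not be able to get different answers from the same data.

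**Working it through.** **Inputs.** Phases of 28, 28 and 14 days (3.3.1); survey allowance of 14 days (3.1.2); start within 2 business days (3.1.3), taken as up to 2 to 4 calendar days with no holiday; up to 7 days to choose a follow-up mode (3.1.4). The documents give no effect size and no distribution of survey delay.

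**The plan's own figure.** Section 3.3.1 gives about three months per subject. With a month of 365.25/12 = 30.44 days:

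- phases alone: 28 + 28 + 14 = 70 days = 2.30 months;
- plus survey allowance and start delay: 70 + 14 + (2 to 4) = 86 to 88 days = 2.83 to 2.89 months;
- plus the mode-choice week, if it lies outside follow-up: 93 to 95 days = 3.06 to 3.12 months.

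The stated duration is approached only when time between phases is counted. This is consistent with gaps being expected, though it does not prove it.

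**Labels or elapsed weeks?**

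- The abstract states that the intervention period is Weeks 5-8. Under labels this is always true; under elapsed weeks it fails for anyone who starts late.
- The end of week 4 and the beginning of week 5 are the same moment. Under labels, week 5 begins when the intervention begins, so the abstract, 3.1.3, 4.3.2 and 7.1.1 agree.
- "during weeks five to ten" spans six weeks, which is intervention plus follow-up (4 + 2). Under elapsed weeks, week 10 ends on day 70, while a latest-allowed starter's intervention ends on day 28 + (16 to 18) + 28 = 72 to 74. Parents' viewing option would lapse before the intervention was over.
- Section 6.3.2 pairs the window with subjects randomized at the intervention's start, which is also the moment of the switch.

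**Size under labels.** Pre-assignment days in the window: 0 of 28. Waiting days are in neither baseline weeks 2 to 4 nor weeks 5 to 8, so 6.3.2 already leaves them out.

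**Size under elapsed weeks.** Let d be the gap in days. Assume even driving across days, a constant effect and a stable control rate. Then observed rate ratio = RR × (1 − d/28) + d/28, and the share of the true percent reduction kept is 1 − d/28. With an assumed true RR of 0.70:

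| Gap d (days) | Share kept | Observed RR |
|---|---|---|
| 0 | 100% | 0.70 |
| 2 | 93% | 0.72 |
| 9 | 68% | 0.80 |
| 16 | 43% | 0.87 |
| 18 | 36% | 0.89 |

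For an assumed mix of 75% of teens at 2 days and 25% at 16 days, the mean gap is 0.75 × 2 + 0.25 × 16 = 5.5 days. The share kept is 80% and the observed RR is 0.76. With unchanged variance, a trial sized on that value would be (ln 0.70 / ln 0.759)² ≈ 1.7 times the size needed. At a mean gap of 2 days the factor is 1.2; at 9 days it is 2.5.

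**The case for a change.** The strongest case for a change is that the primary endpoint should not depend on a label given in the abstract. Section 6.3.2 attaches a period name to the baseline window but not to the second one. A delayed start is foreseeable from the plan's own rules. Control participants show no mode change, so their start cannot be read from the device. One or two sentences would settle the matter.

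Part of this stands: 6.3.2 is terse, and the fixed-week and survey-triggered descriptions were not written to match. The rest carries less weight.

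- **A common anchor exists.** Section 9.1.1 assigns every participant, controls included, on reaching the intervention phase. The assignment date is therefore available in all four arms and does not reveal the arm to a blinded analyst.
- **The missing origin is not fully established.** The study diagram is not reproduced in the text available, and its column headings may carry the timeline.
- **The illustrative mix leans toward delay.** It gives nobody a zero gap, although the start is within 2 business days, and it puts a quarter of teens on the last allowed day. Section 9.7.1 links payment to the baseline survey and section 4.1 provides reminders about incomplete steps; both favour prompt completion.
- **The sizing harm is conditional.** It arises only if the pilot uses the diluted window and the later trial does not.

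**Conclusion.** The concern does not call for a change. The plan omits a date anchor, but its own text supplies the meaning: weeks 5 to 8 are each participant's four-week intervention period, counted from that participant's start. On that reading no pre-assignment driving enters the window and the dilution is zero.

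The elapsed-week reading would put up to 16 to 18 of 28 unblocked days into a single late completer's window. It requires the analyst to set aside the abstract's definition and to accept week numbers in 4.3.2 that no longer fit the phases. Even then the gap precedes assignment, so it should be balanced across arms and would dilute the contrast without favouring an arm. The trial-level size is unknown; the figures for a rate ratio of 0.70 and for the mix of delays rest on assumptions, not on the documents. The stated primary objective is feasibility (section 2.1), and no power calculation or efficacy decision rule depends on this window. Adding an anchor would record the evident meaning and alter no result.
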